# 4.1. Background

Although APP and its downstream products ( $A\beta$  oligomers, c-terminus peptide, and amyloid plaques), and tau neurofibrillary tangles have been well documented to be culprits of AD, recent research has shown that other misfolded proteins are also part of the equation. In AD, in addition to  $A\beta$  and tau, increased levels of  $\alpha$ SYN and TDP-43 have been shown to be correlated with deficits in cognitive functions. A high load of inflammation and microglia activating factors that contribute to neurodegeneration are also common in AD.

Ver. 3.1; 09-25-2023

Buntanetap (Posiphen) is the (+) enantiomer of phenserine, but while phenserine inhibits AChE, buntanetap has no AChE activity itself and develops some activity in vivo with the metabolism to N1-bisnorposiphen. *In vivo*, phenserine has about 10-20 times more AChE inhibitory activity than buntanetap's metabolite N1-bisnorposiphen.

Buntanetap has been found to significantly reduce soluble APP and A $\beta$  as well as tau, p-tau and  $\alpha$ SYN in the rodent brain and in human CSF. In preliminary studies in animals and humans, inhibition of APP, A $\beta$ , tau, p-tau and  $\alpha$ SYN occurs at levels 8 to 16 times lower than the levels causing cholinomimetic effects.

Buntanetap acts at the 5'UTR of the aSYN and APP mRNA and lowers their protein expression levels in animal models; it decreased sAPP $\alpha$  and  $\beta$ , tau, p-tau and aSYN levels in human CSF. Our data suggests that these effects are achieved via the same mechanism: the 5'UTRs of these mRNAs form a complex with iron regulatory protein 1 and buntanetap stabilizes the complex, thereby inhibiting the translation of these mRNAs.

As buntanetap inhibits the synthesis of APP and aSYN, as well as other neurotoxic aggregating proteins, it might have a broader spectrum of activity than AD and PD. By protecting neurons from dying, it has a disease-modifying effect in AD, PD as well as other neurodegenerative disorders.

#### 4.2. Study Overview

**Study population:** The study will be conducted in a diverse population of participants with mild to moderate AD.

**Dose selection**: Qualified participants will be randomly assigned at a 1:1:1:1 ratio to one of the four treatment arms: buntanetap 7.5 mg, buntanetap 15 mg, buntanetap 30mg, and placebo.

**Study Design:** 320 mild to moderate AD participants will be randomized to 7.5 mg, 15 mg, 30mg of buntanetap QD or placebo. If they provide informed consent, they will undergo a Screening Visit, and if they are considered eligible per the inclusion and exclusion criteria, they will proceed to participate in the treatment period. Randomized participants will visit the clinic for the first-time dosing in clinic, followed by an at home dosing period of 12 weeks, with daily administration of 7.5 mg, 15 mg, or 30 mg of buntanetap or placebo. Participants will be required to visit clinics Day 0 (baseline), 6 weeks, and 12 weeks (end-of-trial), where they will

Confidential Page 21 of 57

undergo study procedures that include safety assessments (AE and concomitant medication monitoring, 12-lead ECGs, clinical laboratory testing, vital signs assessments, and physical/neurological examinations) and psychometric tests (ADAS-Cog11, ADCS-CGIC, ADCS-ADL, DSST, MMSE). At the end of blood sampling, the participants will need to stay for a minimum of 1 hour of observation. After all end-of-study procedures are complete, the participant will be discharged to home. A 24-hour follow-up call will occur after all clinical visits to assess the participants current condition and if there are any additional adverse events or questions.

Participants who drop out during the initial 9 weeks at home treatment period will be discontinued and complete an early discontinuation visit as soon as possible following discontinuation. Participants that drop out after the initial 9 weeks will be scheduled for an end of trial visit. If 4 participants are discontinued due to severe adverse events a DSMB safety review will be conducted without interrupting the study.

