#### LIST OF ABBREVIATIONS

5'UTR 5' untranslated regionαSYN Alpha-synuclein

αSYN
 Alpha Synuclein
 Amyloid Beta
 AChE
 Acetylcholinesterase
 AD
 Alzheimer's diseases

ADAS-Cog Alzheimer's Disease Assessment Scale—Cognitive Subscale

ADCS-ADL Alzheimer's Disease Cooperative Study Activities of Daily Living

Inventory

ADCS-CGIC Alzheimer's Disease Cooperative Study Clinician's Global Impression of

Change

AE Adverse Event
ANOVA Analysis of variance
APP Amyloid Precursor Protein

ATC Anatomical Therapeutic Chemical

AUC Area under the curve BChE Butyrylcholinesterase

BDNF Brain derived neurotrophic factor

BP Blood pressure
CA Competent Authority

CFR Code of Federal Regulations

cGMP current Good Manufacturing Practice

CI Confidence Interval CLBP Chronic low back pain

Cmax Maximum plasma and CSF concentration

ChE Cholinesterase

C-SSRS Columbia Suicide Severity Rating Scale

CNS Central Nervous System

CRO Contract Research Organization

CSF Cerebrospinal Fluid CSR Clinical Study Report

CTCAE Common Terminology Criteria for Adverse Events

CV Coefficients of variation
CVD Cerebrovascular Dementia
DNA Deoxyribonucleic Acid

DS Down Syndrome

DSMB Data Safety Monitoring Board

DSM Diagnostic and Statistical Manual of Mental Disorders

DSST Digit Symbol Substitution Test

ECG Electrocardiogram

eCRF Electronic Case Report Form
FCR Fractional clearance rate
FDA Food and Drug Administration
FSR Fractional Synthesis Rate
FWA Federal wide Assurance

GCP Good Clinical Practice

GDPR General Data Protection Regulation

GFAP Glial fibrillary acidic protein

Confidential Page 5 of 57

GI Gastrointestinal

GRAS Generally recognized as safe
GWAS Genome Wide Association Studies

HbA1c Hemoglobin A1C

HEK 293 Human embryonic kidney cells HEENT Head/ears/eyes/nose/throat

hERG Human ether-a-go-go related gene

HIPAA Health Insurance Portability and Accountability Act

HPMC Hydroxypropyl methylcellulose

ICH International Conference on Harmonization

IDMBIndependent Data Monitoring BoardIECIndependent Ethics CommitteeIRBInstitutional Review BoardIREIron-responsible elementIRP1Iron Regulatory Protein 1

LAR Legally authorized representative

MAD Multiple Ascending Dose MCI Mild Cognitive Impairment

MDS-UPDRS MDS-United Parkinson's Disease Rating Scale MedRA Medical Dictionary for Regulatory Activities

mITT modified Intent to Treat

MMRM Mixed model for repeated measures
MMSE Mini-Mental State Examination
mRNA Messenger Ribonucleic Acid

NFL Neurofilament light

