# 3.2. Summary of Clinical Findings

Three Phase 1 studies and two Phase 2a study have been conducted with buntanetap. For the three Phase 1 studies, the first was a single ascending dose (SAD) study in healthy volunteers; the second was a multiple ascending dose (MAD) study in healthy volunteers, and the third one was a pharmacokinetic (PK)/pharmacodynamic study of CSF in mild cognitively impaired participants (Protocol QR12001). One Phase1/2 study (Discover) was to test the safety,

Confidential Page 18 of 57

tolerability, PK and PD of buntanetap in subjects with early Alzheimer's disease (Protocol QR12005). The other Phase 2a study was a double study for both early AD and early PD participants to test buntanetap's safety, pharmacokinetics, biomarkers, and efficacy (Protocol ANVS-12003).

In the SAD trial, buntanetap was administered orally in doses of 10, 20, 40, 80, and 160 mg. Limiting side effects observed following the 160 mg dose resulted in curtailment of the study without administration of the 320 mg dose. The 160 mg dose was associated with an increased incidence of nausea and vomiting (four participants were nauseous and three vomited). Adverse events were either mild or moderate; none were severe. Buntanetap 80 mg was determined as the no observed adverse effect level.

Following oral administration, peak concentration was achieved rapidly, with mean observed  $T_{max}$  between 1.3 and 1.6 hours for both males and females at all doses.  $C_{max}$  increased with increasing dose, as did the various measures of AUC. Differences in mean observed  $C_{max}$  and AUC between males and females at each dose appeared to be related to body weight rather than gender differences.

In the MAD trial, buntanetap was administered orally in doses of 20, 40, and 60 mg 4 times a day (QID). The first two treatments were dosed for 7 days, and the third, for 10 days. Single doses were given on the first and last day to determine the pharmacokinetics of the drug. In general, the drug was well tolerated, resulting in no serious or severe adverse events and only one premature discontinuation, a participant in the 60 mg group discharged because of nausea, vomiting, dizziness and "feeling warm." The incidence of adverse events, all either mild or moderate severity, also occurred with similar frequency in the placebo group. The most common AEs were dizziness, headache, and nausea/vomiting.

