# 6.3. Safety and Tolerability Analysis

Safety and tolerability will be assessed with physical examinations, vital signs, clinical laboratory values, 12-lead ECG, use of concomitant medications, and AE reports. The frequencies of adverse events, serious adverse events, and laboratory abnormalities between the participants across the treatment groups will be compared.

Confidential Page 24 of 57

Participants who dropout during the initial 9 weeks at-home treatment period will be discontinued and invited to an Early Discontinuation visit. Participants that drop out after the initial 9 weeks will be scheduled for an end-of-trial visit. If 4 participants are discontinued due to serious adverse events a DSMB safety review will be conducted without interrupting the study.

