#### 6.12 Adverse Events

Adverse events (AEs) will be coded using MedDRA dictionary, Version 25.1 or newer.

An AE will be considered as a treatment-emergent AE (TEAE) if started after first dose and no later than last dose date + 30 days, or started prior to first dose, but worsened in severity post dose.

The event counts, number and percentage of subjects reporting TEAEs in each treatment group will be tabulated by system organ class (SOC) and preferred term (PT); by SOC, PT and maximum severity; by SOC, PT and relationship to study drug and by descending frequency of PT (within treatment group). If more than one TEAE occurs with the same PT for the same subject, then the subject will be counted only once for that preferred term using the most severe and most related occurrence for the summary. The display in these tables will be sorted alphabetically by SOC and then by descending frequency of PT (within treatment group) within each SOC.

The incidence of most frequently reported (PT frequency >=5% in any group) TEAEs, SAEs reported after treatment start, TEAEs leading to drug withdrawn, and TEAEs related to study drug will be summarized by SOC and PT.

An AE listing by subject will display all events, and will include the verbatim term in addition to the MedDRA SOC and PT. This listing will also include all relevant eCRF data associated with the event: date of onset, date resolved, date of last dose, severity, frequency, outcome and relationship to study drug and action taken with study drug. Separate listings will be presented for subjects with treatment-emergent SAEs, related TEAEs, TEAEs leading to drug withdrawn, fatal TEAEs (if any).

Confidential Page 30 of 57

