## 15 SERIOUS ADVERSE EVENTS (SAE)

#### 15.1 Definition

An SAE is defined as per the US Code of Federal Regulation, Title 21, Part 312.32 (2016) and ICH E2A: International Conference on Harmonization - Tripartite Guideline: Clinical Safety Data Management: Definitions and Standards for Expedited Reporting (1994).

An adverse event or suspected adverse reaction is considered "serious" if, in the view of either the investigator or Sponsor, it results in any of the following outcomes: Death, a life-threatening adverse event, inpatient hospitalization or prolongation of existing hospitalization, a persistent or significant incapacity or substantial disruption of the ability to conduct normal life functions, or a congenital anomaly/birth defect. Important medical events that may not result in death, be life-threatening, or require hospitalization may be considered serious when, based upon appropriate medical judgment, they may jeopardize the participant and may require medical or surgical intervention to prevent one of the outcomes listed in this definition. Examples of such medical events include allergic bronchospasm requiring intensive treatment in an emergency room or at home, blood dyscrasias or convulsions that do not result in inpatient hospitalization, or the development of drug dependency or drug abuse.

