## 20 DATA AND SAFETY MONITORING BOARD (DSMB)

An independent DSMB will review the safety information from the study on an ongoing basis. The DSMB, will identify the study-specific data parameters and format of the information to be reported, as well as the timing of reports based on the enrollment status of the study. The DSMB will initially be provided with data blinded to treatment status, but they may request unblinded data if there is a safety concern.

Ver. 3.1; 09-25-2023

Additionally, the DSMB will be informed of the occurrence of any serious adverse events within 7 days of being reported to the Coordinating Center. The DSMB may at any time request additional information from the Coordinating Center.

Based on the review of safety data, the DSMB will make recommendations regarding the conduct of the study. These may include amending safety monitoring procedures, modifying the protocol or consent, terminating the study, or continuing the study as designed. Using the Safety Review Process (review of lab data, vitals, and adverse events) and the DSMB, there is substantial oversight and case review to alert the investigators, in a timely manner, to any safety issues that may arise. Further details will be provided in the DSMB charter.

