8.10 Data Monitoring

An independent DSMB will review the safety information from the study on an ongoing basis. The DSMB, will identify the study-specific data parameters and format of the information to be reported, as well as the timing of reports based on the enrollment status of the study. The DSMB will initially be provided with data blinded to treatment status, but they may request unblinded data if there is a safety concern.

Additionally, the DSMB will be informed of the occurrence of any SAEs probably related to the drug within 7 days of being reported to the Coordinating Center. The DSMB may at any time request additional information from the Coordinating Center.

The DSMB will consist of at least one statistician and two physicians with experience of DSMBs and clinical trials.

The data to be considered by the DSMB, the process for quality control of reports and data, and the documentation of decisions were described in detail in the mutually agreed DSMB charter prior to the study start. The primary responsibility of the DSMB will be to protect the safety of the study subjects.

Based on the review of safety data, the DSMB will make recommendations regarding the conduct of the study. These may include amending safety monitoring procedures, modifying the protocol or

Version 2.0, 27 February 2024

consent, terminating the study, or continuing the study as designed. Using the Safety Review Process (review of lab data, vitals, and adverse events) and the DSMB, there is substantial oversight and case review to alert the investigators, in a timely manner, to any safety issues that may arise. Further details will be provided in the DSMB charter.

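### Two DSMB safety rules are worded inconsistently: the four-discontinuation trigger (severe versus serious events, Protocol 4.2 and 6.3) and the 7-day SAE notice (Protocol 20 versus SAP 8.10)

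*Protocol*

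**What the plan says.** **The review trigger.** Protocol 4.2 (Study Overview) states: "If 4 participants are discontinued due to severe adverse events a DSMB safety review will be conducted without interrupting the study". Protocol 6.3 (Safety and Tolerability Analysis) states: "If 4 participants are discontinued due to serious adverse events a DSMB safety review will be conducted without interrupting the study". The threshold, the action and the statement that the study continues are the same. One word differs.

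**The two classes.** Protocol 15.1 defines a serious event by its consequence: "it results in any of the following outcomes: Death, a life-threatening adverse event, inpatient hospitalization or prolongation of existing hospitalization", among other outcomes. Severity is a separate attribute, and Protocol 6.12 tabulates events "by SOC, PT and maximum severity" apart from its summary of SAEs. Protocol 3.2, describing the multiple ascending dose study, names both classes: "resulting in no serious or severe adverse events and only one premature discontinuation".

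**The 7-day notice.** Protocol 20 states that "the DSMB will be informed of the occurrence of any serious adverse events within 7 days" of their being reported to the Coordinating Center. SAP 8.10 repeats the sentence with a narrower scope: "the DSMB will be informed of the occurrence of any SAEs probably related to the drug within 7 days".

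**Precedence.** SAP Section 3 says the SAP prevails where it differs from the protocol, and does not confine this to statistical analysis. Protocol 22.1 requires conduct in compliance with the protocol, and 22.2 requires amendments to be approved before use.

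**The concern.** A threshold for convening a safety review should give the same answer wherever it is looked up. Here it does not. The known tolerability problems of this drug are nausea, vomiting and dizziness (Protocol 3.2 and 5.1). Such events can be severe enough to stop treatment without causing hospitalization or another serious outcome. The reverse also occurs: an event of moderate intensity can lead to hospitalization.

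The 7-day notice raises a different question: whether an SAE that the site does not rate probably related keeps a dated route to the DSMB. Sites rate causality one event at a time and under blinding. A DSMB looks for patterns across participants and arms, so a relatedness filter on dated notice works against its purpose. Neither the SAP's version history, which lists only a change to Section 8.8, nor its Section 8.1 on changes explains the narrowing.

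**Working it through.** No formula applies. The two numbers in these rules, 4 participants and 7 days, agree wherever they appear. Only the qualifying words differ, so the check is to set the texts side by side.

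**Trigger: which discontinuations count under each section**

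| Event leading to discontinuation | Counts under 4.2 (severe) | Counts under 6.3 (serious) |
|---|---|---|
| Severe and serious | yes | yes |
| Severe, no serious outcome (e.g. severe nausea managed at home) | yes | no |
| Serious, not severe (e.g. moderate event leading to hospitalization) | no | yes |
| Neither | no | no |

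The sections disagree in the second and third rows. If four participants stop for events of the second kind, a review is due under 4.2 and not under 6.3. If four stop for events of the third kind, it is due under 6.3 and not under 4.2. Both sentences are current text.

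The 4.2 version also has no stated grading basis. Sections 14 and 15 name no severity scale, although the abbreviation list contains "CTCAE Common Terminology Criteria for Adverse Events".

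**Notice: which SAEs carry the 7-day deadline**

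SAP 8.3.1 uses five relatedness ratings.

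| Rating of the SAE | Protocol 20 | SAP 8.10 |
|---|---|---|
| Definitely | yes | not named; presumably intended |
| Probably | yes | yes |
| Possibly | yes | no |
| Unlikely | yes | no |
| Unrelated | yes | no |

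The SAP groups *possibly* with the potentially related events in its own tables (8.3.1), yet 8.10 leaves it outside the dated notice.

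**What still brings the other SAEs to the DSMB**

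- Protocol 14.2: adverse events are reported to the DSMB under Coordinating Center procedures and the charter. No relatedness filter.
- Protocol 15.2: the DSMB is notified once the SAE report is available. No filter, and no day limit on that notice.
- Protocol 20: ongoing safety review, with the right to ask for more information at any time.
- SAP 8.3.1: adverse events go to the DSMB under the charter. No filter.

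None of these routes sets a fixed number of days for the DSMB. What SAP 8.10 puts in doubt is therefore the deadline, not the reporting.

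**The case against.** The best reply on the trigger is that 4.2 and 6.3 do not force a choice. Each states a condition sufficient for a review and neither says *only if*. A team that convenes the DSMB at four severe or four serious discontinuations, whichever comes first, complies with both. That is correct, and it is what the fix writes out. It does not remove the problem: each sentence reads as the complete rule, and nothing in either section points to the other.

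On the notice, informing the DSMB of every SAE within 7 days satisfies both texts. A statistical plan that paraphrases DSMB logistics is a poor vehicle for changing the protocol, given 22.1 and 22.2. This also has force, and it is why the deadline can be read as dropped but is not certainly dropped. The unqualified precedence clause in SAP Section 3 keeps the narrower reading open.

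Oversight also does not rest on these two sentences. The DSMB reviews safety continuously and may request unblinded data (Protocol 20). A safety analysis takes place once 90 randomized participants have been treated for 6 weeks (6.5). Reaching the trigger does not pause the study. SAP 8.10 says the DSMB's data and processes were set out in a charter agreed before the study started, and that charter may settle both points. If it uses a single term for the trigger, however, one of the two protocol sections would still disagree with it.

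Three stronger readings are tempting and not supported:

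- A reader might infer that SAEs not rated probably related are withheld from the DSMB. The four routes listed above show otherwise.
- A reader might infer a sizeable chance of a missed review. The documents give no rate of severe or serious discontinuations. The planned 12.5% dropout covers all causes. Protocol 5.1 reports no SAEs in prior studies, and 3.2 reports no severe events in the single or multiple ascending dose studies, which favours few such discontinuations.
- A reader might infer that the mismatch itself lets three severe-only and three serious-only discontinuations pass without review. That follows from counting two classes separately with a threshold of four each. It would remain under consistent either/or wording.

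**Conclusion.** Both inconsistencies are real and in the current text. They are faults in the wording of safety-oversight rules, not design choices. For the trigger, whether a DSMB review is due can depend on which protocol section is consulted. For the notice, the SAP as written leaves SAEs rated possibly related, unlikely or unrelated without the fixed 7-day deadline that Protocol 20 gives them. They still reach the DSMB, but on no stated timetable.

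The consequence is limited to the clarity and timeliness of safety oversight. No endpoint, estimate, sample size or error rate is affected, and no numerical size can be put on either point from the documents. The conclusion rests on the protocol's own separation of severity from seriousness and on SAP Section 3 being read as it stands. The charter could make both points moot in practice, but the protocol and SAP would still need to agree with it.

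**What to change.** 1. Use one identical sentence in Protocol 4.2 and 6.3, under which the DSMB review is due once four participants have been discontinued for serious adverse events, or four for severe ones, with the study continuing meanwhile. If the charter already uses a single term, put that term in both sections instead.
2. In SAP 8.10, remove the relatedness qualifier so that the 7-day notice covers any serious adverse event, as in Protocol 20.

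Two further edits are optional: naming the severity scale in Protocol Section 14, and confining the precedence clause in SAP Section 3 to statistical analysis.

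The cost is wording edits to two protocol sentences and one SAP sentence, checked against the charter. The either/or trigger adds no review that 4.2 or 6.3 does not already require. There are no new visits, procedures or participants.
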